1.3 Synopsis

Title of the study	Visualisation of changes in regional ventilation in dyspnoeic post-COVID patients - a case-control study using electrical impedance tomography
Acronym	ViReVentPoCov
Director of Studies	Dr. med. [name]
Deputy of the Director of Studies	Priv.-Doz. Dr. med. habil. Dr. [name]
Indication/target population/disease	Post-COVID patients and reference group of lung-healthy subjects
Study design/methodology	
 - monocentric - not controlled; type and number of control groups: 1 - Case-control study (retrospective patient data from routine treatment vs. reference group)
Aims of the clinical trial/objectives	
Primary objective: Examine whether post-COVID patients with dyspnoea show changes in regional ventilation compared to a reference group of lung-healthy subjects.
 
Secondary objectives: To review the indication of EIT in post-COVID patients with dyspnoea.

Study objective	
Primary target figure/main target criterion: There is a difference in regional ventilation between healthy lung patients and post-COVID patients with dyspnoea.
 
Changes in the configuration of the minute image and the regional ventilation delay (RVD) image, the RVD diagram and video-based analysis of the dynamic images
 
Secondary target variables/ secondary target criteria: Review of the indication for an EIT examination in patients with post-COVID syndrome

Number of patients	
Number in analysis: n=20 post-COVID patients / n=80 healthy lung patients
 
Considering the first comparison of EIT data of post-COVID patients with those of a reference group, no formal calculation of the number of patients is calculated and a patient number of n=20 and a subject number of n=80 are assumed to be sufficient. The number of subjects is planned to be higher than the number of patients so that enough reference values of EIT in the different age groups can be analysed and compared with those of the patients in the age-adjusted comparison.

Inclusion criteria	EIT data of post-COVID patients with dyspnoea from the post-COVID outpatient clinic of university hospital Jena (retrospective) and lung-healthy non-smokers without resting or exertional dyspnoea (both groups breathing spontaneously).
Exclusion criteria	
 - Pacemaker - BMI over 50, here the PulmoVista® 500 system should not be used according to the manufacturer. - uncontrolled body movements

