4.5 Patient recruitment

- Accessibility of the intended number of patients:
- Given by retrospective analysis of EIT data of post-COVID patients from the UKJ outpatient clinic (planned n=20).
- Number of participants: n=80 subjects
- Procedure for recruiting examination candidates: Addressing UKJ staff/students

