6.2 Exclusion criteria

- Pacemaker wearers
- BMI over 50, here the PulmoVista® 500 system should not be used according to the manufacturer
- uncontrolled body movements

7. Process of the study

- Recruitment of lung-healthy subjects (UKJ staff/students)
- Formation of the reference group: for each subject, conduct an EIT examination in a quiet and distraction-free environment (single room ZNA) to avoid artefacts.
- Post-COVID patients: retrospective analysis of EIT data
- Comparison of the EIT parameters of the two groups

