9.1 Endpoints

9.3 Planning the scope of the study (caseload planning)

Considering the first comparison of EIT data of spontaneously breathing lung-healthy subjects compared to patients with dyspnoea in the context of a post-COVID syndrome, a subject number of n=80 and patient number of n=20 each is assumed to be sufficient for the investigation of significant differences. The number of subjects is planned to be higher than the number of patients so that enough reference values of EIT in the different age groups can be analysed and compared with those of the patients in the age-adjusted comparison.

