9.4 Statistical evaluation

The comparison of the 32x32 pixel matrices of the EIT images [tidal images] and the comparison of the relative distribution of the breath volume across the ROIs is done with the Wilcoxon rank sum test.

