10.1 Patient identification list

All patient-related data is recorded in pseudonymised form. For this purpose, a non-speaking pseudonym is used, from which alone the identity of the patient cannot be inferred. In order to obtain unique patient identification numbers, a combination of a fixed trial centre number and a consecutive centre-specific patient number is chosen.

The trial centre maintains a patient identification list in which the patient identification numbers are linked to the full patient names of the participants, patient identification number and date of birth, if applicable. This list serves the possibility of later identification of participating persons. It will be kept absolutely confidential and will not leave the trial centre. It will be archived for **at least ten years** after the end of the study.

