10.7 Data protection

Within the framework of the study, it is necessary to collect and process personal data from the study participants (e.g. full name, initials of first and last name, date of birth, address) and data on the course of the disease (e.g. medical findings, types of treatment, prescribed medication). These data are collected at the trial centre and stored electronically in pseudonymised form (i.e. without direct reference to the patient's name) with the help of a patient identification number, transmitted to the responsible data-processing agency and evaluated.

In the event of a revocation of consent to the study by the patient, including further data collection, no further data will be collected from the time of revocation. The data collected so far will continue to be used and evaluated within the study. If a patient only discontinues the study treatment, the data required for the study can continue to be collected and used.

11. ethical concerns, legal and administrative regulations

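### Section 9.4 names only a rank sum test with no age term, although an age-adjusted comparison is the stated reason for 80 reference subjects; no adjustment method is given

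*Combined protocol and SAP*

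**What the plan says.** The sample size rests on age. Section 9.3 explains that there are more reference subjects than patients so that reference values across age groups "can be analysed and compared with those of the patients in the age-adjusted comparison". The synopsis gives the same reason, with the values "compared with those of the patients in the age-adjusted comparison".

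Section 9.4 is a single sentence. It applies one test to the tidal-image pixel matrices and to the ROI shares: the "comparison of the relative distribution of the breath volume across the ROIs is done with the Wilcoxon rank sum test". Section 3.1 makes the ROI distribution the primary endpoint, so this is the primary analysis. Section 7 (Process of the study) adds only "Comparison of the EIT parameters of the two groups".

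On who is compared, section 4.5 takes the patients from existing outpatient clinic records. For the reference group it states "Procedure for recruiting examination candidates: Addressing UKJ staff/students". The only age rule is adulthood (section 5.1). There is no age quota, matching or upper limit.

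**The concern.** A two-sample rank sum test compares two whole groups and cannot hold age constant. The plan announces an age-adjusted comparison, builds its group sizes on it, and then does not say how it will be done.

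Two things are at stake. First, an analyst who follows 9.4 word for word runs an unadjusted comparison of two groups recruited in different ways. An age difference could then pass for a post-COVID effect or cancel one. Second, an analyst who follows 9.3 must invent the adjustment. Age bands, matching and regression are all open, and a choice made after seeing the results could follow them. Either way the primary result is harder to defend than it need be.

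**Working it through.** **The text.** The documents were checked for any age band, stratum, matching rule, covariate model or age-specific reference limit; none appears. Heading 9.1 has no text and there is no 9.2. That may be a gap in the available text, so no weight is put on it. Section 9.4, where the method belongs, is present.

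**Inputs from the documents.** 20 patients and 80 reference subjects (sections 4.4 and 9.3). No alpha, power, effect size or SD is given, and the synopsis says that no formal calculation was made, so there is no planned figure to reproduce.

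**Assumptions, none from the documents.** Two-sided 5% test; normal data; linear age effect; mean age gap *g* of 0 to 1.5 within-group SDs of age; within-group correlation *r* between age and endpoint of 0 to 0.5.

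**Bias.** The unadjusted comparison picks up a spurious shift of *r* × *g* SD. The standard error of the group difference is √(1/20 + 1/80) = 0.25 SD. With Wilcoxon efficiency 0.955 (√0.955 = 0.977), the expected test statistic is 0.977 × *r* × *g* / 0.25. Three cells with no true effect:
- *g* = 0.5, *r* = 0.2: 0.977 × 0.10 / 0.25 = 0.39, rejection about 6.8%.
- *g* = 1.0, *r* = 0.3: 0.977 × 0.30 / 0.25 = 1.17, rejection about 21.6%.
- *g* = 1.5, *r* = 0.5: 0.977 × 0.75 / 0.25 = 2.93, rejection about 83%.

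Simulation of the rank sum test (20,000 runs per cell) agrees. The power rows take a true shift of 0.73 SD opposed by the age effect; with no age gap its power is about 80%.

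| Age gap | Quantity | r = 0.2 | r = 0.3 | r = 0.5 |
|---|---|---|---|---|
| 0.5 SD | false positives | 6.9% | 8.7% | 15.6% |
| 1.0 SD | false positives | 12.0% | 21.0% | 48.4% |
| 1.5 SD | false positives | 20.9% | 41.0% | 82.2% |
| 0.5 SD | power | 68% | 60% | 45% |
| 1.0 SD | power | 54% | 39% | 14% |
| 1.5 SD | power | 38% | 19% | 5% |

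With *g* = 0 or *r* = 0 the false-positive rate is about 5%.

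**With age in the analysis.** Under the null, a linear model on group and age with ordinary standard errors rejects in 4.7 to 5.3%, and with HC3 robust standard errors in 4.4 to 5.5%. Power of the ordinary model for the 0.73 SD shift is 71 to 91%. A van Elteren test depends on band width. In the most extreme cell (*g* = 1.5, *r* = 0.5), three bands still reject in 12.2% and five in about 6 to 7%.

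**Price of adjusting.** Unadjusted, the difference detectable with 80% power is 2.80 × 0.25 = 0.70 SD. The regression multiplies this by √[(1 + 0.16*g*²)(1 − *r*²)], where 0.16 = 0.2 × 0.8 from the 20:80 split.
- Lowest (*g* = 0.5, *r* = 0.5): √(1.04 × 0.75) = 0.883, so 0.62 SD (-12%).
- Highest with age relevant (*g* = 1.5, *r* = 0.2): √(1.36 × 0.96) = 1.143, so 0.80 SD (+14%).
- Age irrelevant (*r* = 0, *g* = 1.5): √1.36 = 1.166, so 0.82 SD (+17%).

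This formula ignores the further penalty from robust standard errors and the t distribution.

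**The case against.** The strongest reply is that the sections are compatible. Section 9.3 speaks of age groups and 9.4 names the test, so a rank sum test within age groups may be what is meant. That is a fair reading. A reader might infer that 9.4 contradicts 9.3; the documents do not support this, because nothing in 9.4 says that ages are to be pooled. What stands against the reply is that the within-group reading has no cut-points and no rule for combining groups. It cannot be carried out without decisions that the plan leaves open.

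A reader might also infer that age will not be available. The identification list holds "patient identification number and date of birth, if applicable", but that wording concerns the list, not the analysis dataset. Section 10.7 gives as examples of the personal data collected "full name, initials of first and last name, date of birth, address", the visit plan includes baseline data, and adulthood has to be checked. Age is very probably obtainable; it is simply not named as an analysis variable.

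Finally, the harm is assumed. The documents give no ages and no relation between age and EIT measures, and the striking figures come from the far corner of the grid. That is right, and the table should not be read as a forecast that the result will be biased. But the plan's own call for age adjustment shows that age was thought to matter, and nothing in the recruitment makes the groups alike in age.

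**Conclusion.** The point holds as a missing method for the primary comparison, and it should be settled before the analysis. It is certain that the documents state the intent to adjust for age and give no means of doing so, and that the one named test has no age term. It is conditional that the result would be biased: this needs both an age gap and an age effect on ROI shares. If either is absent there is no inflation. With a small gap and weak correlation it is slight (about 7% against a nominal 5%). With a 1 SD gap and a correlation of 0.3, about one null comparison in five would be declared significant. The upper figure of 82% needs a 1.5 SD gap and a correlation of 0.5. Direction is unknown, so masking is as possible as a false finding. All sizes rest on the normal, linear model and the 20 versus 80 split.

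**What to change.** In 9.4, name one age-adjusted method as the primary ROI analysis, fixed before the two groups are compared. Either of these would do:
- Regress each ROI share on group and age in years with robust (HC3) standard errors, and report the age-adjusted group difference in percentage points with its 95% CI.
- Use a van Elteren (stratified Wilcoxon) test with prespecified age bands. This stays closest to the present wording, but the bands must be narrow enough; three were too coarse at the largest gap and correlation examined.

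Keep the unadjusted Wilcoxon test as a supporting analysis. If the pixel comparison is inferential, give it the same adjustment. State that age at the EIT examination is carried into the analysis dataset for every participant.

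The drafting cost is a few sentences and one variable. The statistical cost of the regression is the -12% to +14% change in detectable difference shown above, or up to +17% if age proves irrelevant and the gap is 1.5 SD. A banded test loses more power when the age gap is large. No adjustment repairs a lack of age overlap, so the age distributions of both groups should be reported. Multiplicity over ROIs is a separate point with its own power cost, and age adjustment does not depend on it.

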9.5 Interim evaluation(s)

- none planned

10. data management

10.1 Patient identification list

All patient-related data is recorded in pseudonymised form. For this purpose, a non-speaking pseudonym is used, from which alone the identity of the patient cannot be inferred. In order to obtain unique patient identification numbers, a combination of a fixed trial centre number and a consecutive centre-specific patient number is chosen.

The trial centre maintains a patient identification list in which the patient identification numbers are linked to the full patient names of the participants, patient identification number and date of birth, if applicable. This list serves the possibility of later identification of participating persons. It will be kept absolutely confidential and will not leave the trial centre. It will be archived for **at least ten years** after the end of the study.

10.2 List of responsibilities

A signature list with the name, function in the study, study-related activity and abbreviations of the responsible persons is filed in the study centre folder.

10.3 Data collection/documentation forms

To achieve the study objective, it is necessary to collect and process medical data from individual patients. Data collection takes place at the trial centre involved in the study. The data collection is paper-based.

10.4 Data processing

- takes place pseudonymised in Excel, SPPS and MatLAB

10.6 Study documents and their storage (archiving)

The originals of all essential study documents shall be retained by the study director for at least ten years after the preparation of the final report.

At the trial centre, the accrued administrative documents (e.g. correspondence with ethics committee(s), study management), the patient identification list, the signed consent forms and the general study documentation (study protocol, amendments) are stored for the above-mentioned period. All documentation will be kept securely and treated confidentially. The patient identification list will be kept separately from the documentation records.

Original study patient data (e.g. medical records) or essential study documents shall be retained in accordance with the archiving period applicable to the trial sites, but not less than ten years). The trial site or the responsible person shall take precautions to prevent the accidental or premature destruction of these documents.

10.7 Data protection

Within the framework of the study, it is necessary to collect and process personal data from the study participants (e.g. full name, initials of first and last name, date of birth, address) and data on the course of the disease (e.g. medical findings, types of treatment, prescribed medication). These data are collected at the trial centre and stored electronically in pseudonymised form (i.e. without direct reference to the patient's name) with the help of a patient identification number, transmitted to the responsible data-processing agency and evaluated.

In the event of a revocation of consent to the study by the patient, including further data collection, no further data will be collected from the time of revocation. The data collected so far will continue to be used and evaluated within the study. If a patient only discontinues the study treatment, the data required for the study can continue to be collected and used.

11. ethical concerns, legal and administrative regulations

11.1 Declaration of Helsinki and Good Clinical Practice

The study will be conducted in accordance with the ethical principles originating in the Declaration of Helsinki [Ref.]. The current version of the Declaration will be observed.

The recommendations of Good Clinical Practice [Ref.], valid since 17.1.1997, are taken into account where applicable.

11.2 Ethics Committees

The study protocol is submitted with the required further documents to the responsible lead ethics committee of the study director with a request for evaluation. The study can only begin after the Ethics Committee has given its approval.

The Ethics Committees of the participating trial centres receive a copy of the positive evaluation of the first Ethics Committee and the documents required for the "second vote". Each participating trial site will receive copies of the positive evaluation of the first ethics committee and of its responsible ethics committee for the trial site file.

11.3 Subsequent changes

The study protocol must be adhered to. Any deviation from the planned examination and treatment measures or times for which the investigator is responsible must be documented and justified (e.g. emergency measures).

Changes or additions to the study protocol can only be initiated and authorised by the study management. The lead ethics committee and the ethics committees of the participating trial centres will be informed of any changes to the study protocol. If necessary, their approval will be sought again. Changes requiring evaluation may not be implemented before the decision of the ethics committee.

Changes to the study assessed by the Ethics Committee that are appropriate,

- have an impact on the safety of the persons concerned,
- additional data collection or evaluations that require a change in patient information and/or consent,
- influence the interpretation of the scientific documents on which the study is based or the scientific validity of the study results,
- substantially change the way the study is managed or conducted,

may only be made if these changes have been approved by the Ethics Committee.

11.4 Legal regulations

11.5 Patient insurance/proband insurance

-not applicable

11.6 Registration

The study is to be registered in the following public register: www.clinicaltrial.gov.

11.7 Funding

The study is financed through budgetary funds.

